4.2.1. Treatments Administered

Dosing of the medications does not need to occur at the same time. All subjects receive remdesivir as a 200 mg intravenous (IV) loading dose on Day 1, followed by a 100 mg once-daily IV maintenance dose for the duration of the hospitalization up to a 10-day total course. If subjects already received the loading dose prior to study enrollment, then start at 100 mg/day on Day 1. Any doses of remdesivir given prior to enrollment will be counted, so the total duration of remdesivir (i.e. pre-enrollment + on this trial) is 10 days (i.e., a maximum of 10 total infusions). Any doses of remdesivir were administered prior to study enrollment should be documented in Advantage eClinical as a concomitant medication given prior to Day 1. The duration of dosing may be adjusted by the site similar to what is described in the package insert and based on a subject's clinical course and ultimate disease severity.

For the baricitinib component, subjects receive either active product or placebo as follows:

- Baricitinib will be administered as a 4 mg orally (po) (two 2mg tablets) or dissolved for NG tube, daily for the duration of the hospitalization up to a 14-day total course.
- A placebo will be given as two tablets po or dissolved for NG tube, daily for the duration of the hospitalization up to a 14-day total course.
 - Any pre-study dexamethasone (max 1 dose per inclusion criteria) is not counted towards the 10-day course.

For dexamethasone component, subjects receive either active product or placebo as follows:

- Dexamethasone administered as a 6 mg slow IV push over 3 to 5 minutes daily for the duration of the hospitalization up to a 10-day total course.

- A placebo will be given as an equal volume normal saline, as a slow IV push daily for the duration of the hospitalization up to a 10-day total course.
- If site local standards use other means of administration (such as IV infusion), these may be used for both active and placebo after approval of the sponsor.
- Any pre-study dexamethasone (max 1 dose per inclusion criteria) is not counted towards the 10 day course.

Duration of therapy:

- IV remdesivir – up to 10 days while hospitalized (i.e., maximum of 10 total infusions pre-enrollment and during study).
- Oral baricitinib (or oral placebo) – 14 days while hospitalized (i.e., maximum of 14 total doses).
- IV dexamethasone (or IV placebo) – 10 days while hospitalized (i.e., maximum of 10 total doses).

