There will also be a sensitivity analysis of the primary, secondary, and mortality outcomes to evaluate the effect of concomitant therapy including experimental treatment and off-label use of marketed medications that are intended as treatment for COVID-19 and are given to patient prior to and during the study. A blinded review of the concomitant medication data will be performed by the medical monitor to identify medications that fall into any of the following categories of “Medications of Interest”:

- Vaccine for SARS-CoV-2 (Pfizer, Moderna, or other) including 1 or 2 doses received
- Antivirals
 - Protease inhibitors
 - Polymerase inhibitors
- Other Potential Treatments for COVID-19
 - Aplidin® (plitidepsin)
 - Colchicine (Colcrys)
 - Monoclonal antibodies targeting the spike protein of SARS-CoV-2 including casirivimab, imdevimab and bamlanivimab
 - Ivermectin (stromectol, Soolantra, Sklice)
- Corticosteroids
- Renin-angiotensin system (RAS) Inhibitors and HMG-CoA reductase inhibitors (statins)
- Other anti-inflammatory drugs
 - Monoclonal Antibodies Targeting Cytokines
 - Other Biologic Therapies

Summaries of subjects who report use of the categories and subcategories of therapies/treatments will be provided. Note that after the blinded review of the medications, additional categories/sub-categories may be defined and/or categories/sub-categories may be combined.

In addition, the sensitivity analyses will consider the following categories (individually):

- Any Medication of Interest
- Vaccines to SARS-CoV-2
- Antivirals
- COVID-19 treatments
- Monoclonal antibody treatments for COVID-19
- Corticosteroids
- RAS Inhibitors and HMG-CoA reductase inhibitors (statins)
- Other Anti-Inflammatory Drugs

Three initiation and duration groups will be constructed for each of the above categories:

1. Prior and During: Subjects taking medication of interest before randomization and during study (on or after Day 1).
2. Prior Only: Subjects taking medications of interest prior to randomization but stopping prior to randomization.
3. During Only: Subjects initiating medications of interest during the study (on or after Day 1).

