For the analysis of mechanical ventilation free survival, subjects will be censored at the time of medication/therapy initiation. For the analysis of the key secondary outcome, if a subject reports use of any of the medications/therapies prior to their Day 15 assessment, then the subject's last clinical status score prior to medication/therapy use will be used as their Day 15 outcome. For the mortality analyses, subjects will be censored at the time of medication/therapy initiation. For the analysis of the proportion of subjects that do not progress to Clinical Status Ordinal Score of 6, 7, or 8 by Day 29, subjects will be censored at the time of medication / therapy initiation. For the recovery analyses, subjects will be censored at the time of medication/therapy initiation. If a subject recovered prior to use of any of the medications/therapies, then the subject will still be counted as a recovery in the sensitivity analysis.

The effect of on-study treatment on select efficacy outcomes will also be explored among subjects who reported use of HMG-CoA reductase inhibitors (statins), angiotensin receptor blockers (ARBs), or angiotensin converting enzyme inhibitors (ACEIs) via subgroup analyses.

Lastly, the effect of treatment on the primary and key secondary efficacy outcomes will be explored via regression modeling controlling for age, duration of symptoms prior to randomization, baseline d-dimer, and baseline CRP values as continuous covariates.

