9.1.2. Prior and Concomitant Medications

Medication history (concomitant medications) includes a review of all current medications and medications taken within 7 days prior to enrollment through approximately Day 15 or early termination (if Day 15), whichever occurs first.

Summaries of medications that were started prior to dosing and continued at the time of dosing or started after dosing while on study will be presented by WHO Drug Level 1 and 2 Codes, actual baseline ordinal score, and treatment group ([Table 57](#)). Summaries of overall use of medications/therapies of interest listed in Section [6.4](#) that were started prior to dosing and continued at the time of dosing or started after dosing while on study as well as use by select study days will also be generated ([Table 58](#) and [Table 59](#)).

Individual subject listings will be presented for all concomitant medications ([Listing 9](#)), corticosteroid use ([Listing 10](#)), and medications of interest ([Listing 11](#)).

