Table 18: Mechanical Ventilation Free Survival by Day 29 by Treatment Group: Prior Corticosteroid Use – mITT Population, Actual Baseline Ordinal Score 5 or 6

Table 19: Mechanical Ventilation Free Survival by Day 29 by Treatment Group: Medications of Interest Sensitivity Analysis – mITT Population, Actual Baseline Ordinal Score 5 or 6

Programming Notes for Table 17:

A “Subgroup” column will replace the “Model” column to the left of the “Treatment Group” column. Actual baseline ordinal score subgroups, prior corticosteroid use and medications of interest will not be included in this table. This table will include all other subgroups (see Section 6.4). P-values will not be included in this table.

Programming Notes for Table 18 and Table 19:

P-values will not be included in these tables.

A “Subgroup” column will replace the “Model” column to the left of the “Treatment Group” column. Actual Baseline Ordinal Score subgroups will not be included in this table.

A “Subgroup” column will replace the “Model” column to the left of the “Treatment Group” column. Actual Baseline Ordinal Score subgroups will not be included in this table. Separate models will be fit with censoring based on the first date of use for each of the following categories of medications (see Section 6.4).

- Any Medication of Interest
- Antivirals
- COVID-19 Vaccination
- Treatments for COVID-19
- Monoclonal antibodies targeting the spike protein of SARS-CoV-2 including casirivimab, imdevimab, and bamlanivimab.
- Renin-angiotensin system (RAS) Inhibitors and HMG-CoA reductase inhibitors (Statins)
- Corticosteroids
- Other Anti-Inflammatory Drugs

The table will include the following footnote: "In this analysis, subjects that reported use of the specified medications of interest are censored at time of medication receipt."

Table 20: Summary of Recoveries, Ventilator/ECMO Requirement, and Deaths by Day 29 – mITT Population

Grouping Variable	Actual Baseline Ordinal Score	Treatment Group	Recovered		Not Recovered and do not Require Mechanical Ventilation or ECMO		Require ECMO		Require Mechanical Ventilation		Require Mechanical Ventilation or ECMO		Deaths		
			n	%	n	%	n	%	n	%	n	%	n	%	
Actual Baseline Ordinal Score	5	Baricitinib + PBO + RDV (N=X)	x	x	x	x	x	x	x	x	x	x	x	x	
		PBO + Dexamethasone + RDV (N=X)	x	x	x	x	x	x	x	x	x	x	x	x	
	6	Baricitinib + PBO + RDV (N=X)	x	x	x	x	x	x	x	x	x	x	x	x	
		PBO + Dexamethasone + RDV (N=X)	x	x	x	x	x	x	x	x	x	x	x	x	

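### The medication-of-interest sensitivity analyses censor at first use without separating pre-randomization from on-study starts, and the Day 15 version overwrites observed deaths and ventilation

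*SAP*

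**What the plan says.** Section 6.4 brings into scope drugs intended as COVID-19 treatment that are given before and during the study. The categories include vaccines, antivirals (with polymerase inhibitors), corticosteroids, RAS inhibitors/statins and other anti-inflammatory drugs. The section defines three timing groups for each category: Prior and During, Prior Only, and During Only. No analysis rule then refers to these groups.

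The rules that follow are:

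- **Ventilation-free survival:** "For the analysis of mechanical ventilation free survival, subjects will be censored at the time of medication/therapy initiation". Progression to category 6, 7 or 8 is handled in the same way.
- **Mortality:** "For the mortality analyses, subjects will be censored at the time of medication/therapy initiation".
- **Recovery:** "For the recovery analyses, subjects will be censored at the time of medication/therapy initiation"; a recovery that precedes use still counts.
- **Day 15 score:** for a subject reporting use before the Day 15 assessment, the "last clinical status score prior to medication/therapy use will be used as their Day 15 outcome".

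The programming notes for Tables 18/19, 26/27, 32 and 73 say: "Separate models will be fit with censoring based on the first date of use". The categories listed there include vaccination, RAS inhibitors/statins and corticosteroids.

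Three other sections bear on this. Section 3.3.3 starts the clock at randomization. Section 4.2.1 allows one pre-study dexamethasone dose and says that earlier remdesivir doses "should be documented in Advantage eClinical as a concomitant medication given prior to Day 1". Section 9.1.2 limits the medication history to "medications taken within 7 days prior to enrollment through approximately Day 15".

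**The concern.** Two different situations are put under one censoring rule.

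**Use that began before randomization.** A start date earlier than the time origin gives a censoring time at or below zero, so the subject is never at risk. For the Day 15 rule no post-randomization score precedes the use. A programmer would have to drop the subject, move the start to Day 1 or ignore the prior use, and these choices give different analysis sets. The notes for Tables 18 and 26, which are about prior corticosteroid use, share the censoring text with Tables 19 and 27. Taken literally, those tables would censor the very subjects they are meant to describe.

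**Use that began on study.** If a listed drug is started at category 5 or 6 because the subject is getting worse, censoring removes the event about to happen. For mortality, a drug started after ventilation censors a later death; Section 4.2.6 expects treatment to be reconsidered at category 7. In the Day 15 analysis, a recorded 7 or 8 is replaced by an earlier and often better score.

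At stake is whether Tables 19, 21, 27, 32 and 73 can be read as support for the main results.

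**Working it through.** **Inputs from the SAP (Section 5, Table 1).** N = 1382 (691 per arm), event-free proportions 0.85 and 0.90, two-sided 5%, stated power 80% (exact score) and 80.5% (Kaplan-Meier with Greenwood variance). The SAP gives no share of prior users and no share of events preceded by a drug start. All such shares below are assumptions.

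**Reproducing the plan's figure.** Pooled normal approximation:

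power = Φ{[0.05 − 1.96·√(2·0.875·0.125/691)] / √[(0.85·0.15 + 0.90·0.10)/691]} = Φ{(0.05 − 0.0349)/0.0177} = 80.3%.

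The unpooled form gives 80.5%. Both agree with Table 1.

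**Step 1: prior users drop out.** Let f be the share of prior users. N left = 1382·(1 − f), and standard errors grow by 1/√(1 − f). Power at the design effect serves only as a scale for lost information, since these tables carry no treatment p-value.

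| f (assumed) | N left | SE factor | Power |
|---|---|---|---|
| 0 | 1382 | 1.00 | 80% |
| 10% | 1244 | 1.05 | 76% |
| 25% | 1036 | 1.15 | 68% |
| 50% | 691 | 1.41 | 51% |
| 75% | 346 | 2.00 | 29% |

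**Step 2: on-study starts just before the event, equal shares.** Simulation of 2000 trials, 691 per arm, unstratified Kaplan-Meier estimate at Day 29 with the complementary log-log test. Initiation is placed one day before the event, and 5% (first row) or 10% (other rows) of event-free subjects also start a drug at a random time. With no medication censoring the simulation returns 0.849 and 0.900, power 81%.

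| Events preceded by a start (both arms) | Estimated proportions | Difference |
|---|---|---|
| 20% | 0.877 vs 0.918 | 0.041 |
| 40% | 0.905 vs 0.937 | 0.033 |
| 60% | 0.936 vs 0.957 | 0.022 |

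Both arms look better than they are, and the difference shrinks from 0.050.

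**Step 3: unequal shares, no true effect (0.85 in both arms; 10% of event-free subjects also start a drug).**

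| Shares, arm A vs arm B | False difference |
|---|---|
| 20% vs 30% | 0.015 |
| 20% vs 40% | 0.029 |
| 20% vs 60% | 0.060 |

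A hand check uses an event rate of 12.5%, the mean of the design rates 15% and 10%. If a share r of events is censored first, the apparent rate is 0.125·(1 − r).

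- r = 50% vs 70%: 6.25% vs 3.75%, HR = ln(0.9625)/ln(0.9375) = 0.59.
- r = 40% vs 60%: 7.5% vs 5.0%, HR = ln(0.95)/ln(0.925) = 0.66.

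These hazard ratios only illustrate the assumed unequal shares.

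**Step 4: capture window.** Medication starts are collected to about Day 15, while the time-to-event analyses run to Day 29. A later start is not recorded, so that subject stays uncensored. Section 9.1.2 states the window, but the affected tables carry no note of it.

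**The case against.** The strongest reply is that the SAP does not say in words that prior users are censored. Section 6.4 uses the word for initiating only in the During Only group, defined as on or after Day 1, and the Day 15 and recovery rules make most sense for on-study starts. That is a fair reading of intent. It does not settle the matter, because the shells say first date of use and the timing groups have no rule attached.

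Several stronger readings are tempting, and the SAP does not support them:

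- **That these are the only analyses addressing such use.** The main mITT analysis applies no medication censoring, so it already counts events after a drug start. Section 6.4 also plans subgroups for prior corticosteroids and for statin/ARB/ACEI users.
- **That most of the trial may be discarded.** No usage figure in the SAP supports this.
- **That pre-enrolment remdesivir will be counted as an antiviral.** It is recorded as a concomitant medication, but it is background treatment for every subject, has its own table (Table 9), and a blinded medication review decides the classification. The text leaves it open; it does not say it will be counted.
- **That the censoring favours one arm.** The trial is double-blind, and unblinding for worsening is offered only at category 7, which is already a primary event. Nothing in the SAP predicts an imbalance in earlier starts. Equal shares attenuate the difference (step 2).
- **That a composite must replace the censoring.** Counting every start as an event brings its own bias. With 12.5% true events in both arms and an assumed 5% vs 10% of event-free subjects starting a drug, the rates become 0.125 + 0.875·0.05 = 16.9% and 0.125 + 0.875·0.10 = 21.3%, so HR = ln(1 − 0.2125)/ln(1 − 0.16875) = 1.29.

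It also stands that Section 8.2 calls these analyses supportive and places them outside the testing hierarchy. The medication tables, and the medication rows of Table 21, show no treatment p-value.

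**Conclusion.** The point holds as a defect in the rules for a set of supportive analyses. Read literally, prior users contribute nothing to the time-to-event versions and have no on-study score for the Day 15 version. Censoring at on-study starts may be informative, and the Day 15 rule discards observed deaths and ventilation. That starts are driven by worsening is an inference, since the SAP gives no reasons for use. For the primary endpoint it matters only for starts at category 5 or 6.

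Under the assumed shares, the effect runs from slight (10% prior users, standard errors 5% larger) to substantial (20% vs 40% of events preceded by a start, a false difference of 0.029, more than half the design difference). The primary test, its type I error and its power are untouched. The change is worth making because it is cheap and the tables are hard to interpret without it.

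**What to change.** 1. Use the three timing groups already in Section 6.4. Apply medication censoring only to first starts on or after Day 1, and treat prior use as a baseline subgroup for every category, as is already planned for prior corticosteroids and statins/ARBs/ACEIs. Align the programming notes, and separate those for Tables 18 and 26 from the censoring text.
2. State that pre-enrolment remdesivir is not counted under Antivirals.
3. In the Day 15 analysis keep an observed death as category 8 and an observed ventilation as category 7, instead of carrying the pre-use score forward.
4. Label the time-to-event results as subject to informative censoring, present them beside the uncensored mITT results (including mortality), and footnote that starts after about Day 15 are not captured.

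A composite endpoint or inverse-probability-of-censoring weighting may be added but is not needed.

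The cost is SAP wording and minor reprogramming of supportive tables (mainly 19, 21, 27, 32 and 73). No new data are needed, and the primary analysis does not change.

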Note that the interim efficacy analyses will be performed using R. For all interim and final analyses, the software used will calculate the test statistic using the formula in Section 8.1.1.

To perform a stratified Cox proportional hazards model for the final analysis and generate the treatment arm hazard ratio along with its confidence interval, the following pseudocode will be used. For any unstratified analyses, code can be used after the removal of the `strata ... ;` line and strata variable in the `class` statement.

```
proc phreg data=dataset;
  class StrataVariable(ref=StrataLabel) TreatmentVariable(ref=Dxa_RemdesivirLabel);
  model TimeVariable * CensorVariable(1) = TreatmentVariable;
  strata StrataVariable;
  hazardratio TreatmentVariable / diff=ref cl=Wald;
  ods output HazardRatios = HRest;
run;
```

The following SAS pseudocode will be used to perform the proportional odds model with treatment arm and actual baseline ordinal score as covariates and to generate the treatment odds ratio, p-value, and predicted probabilities of the ordinal scale levels by treatment arm and actual baseline ordinal score:

```
proc logistic data=dataset
  plots(only)=effect(x=ResponseVariable sliceby= actualbaselinestrata
    *TreatmentVariable individual connect);
  class actualbaselinestrata(param=ref ref=category5)
    TreatmentVariable(param=ref ref=RemdesivirLabel);
  model ResponseVariable = TreatmentVariable StrataVariable;
  odsratio TreatmentVariable;
  ods output OddsRatiosWald = ORest;
run;
```

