8.1.2. Hierarchical Sequence of Secondary Endpoints Analyses

Analyses described in this section will be subject to the fixed-sequence hierarchical testing procedure described in Section 6.8. Any reference to p-values in this section is conditional on preceding hypothesis tests in the hierarchy.

If a superior test fails to reject the null hypothesis, the analyses will still be performed to provide estimated effects with confidence intervals for relevant statistics and associated confidence-interval by-arm, but p-values will not be generated. Confidence intervals for all analyses of secondary endpoints, will be 95% confidence intervals.

8.1.2.1. Clinical Status Ordinal Scale at Day 15

In the mITT population, the distribution of the 8-point Clinical Status ordinal score at Study Visit Day 15 (not necessarily actual study day 15), will be analyzed using a proportional odds model with treatment arm and actual baseline ordinal score (baseline ordinal score 5 or baseline ordinal score 6) as covariates. The treatment odds ratio estimated from the model will be presented along with the p-value, (Table 21). This analysis will be repeated for the As Treated population (Table 22). The Study Visit Day 15 clinical status score will be depicted graphically using shifted bar plots; the outcomes will be presented by actual baseline ordinal score and treatment group (Figure 13).

8.1.2.2. Proportion of Subjects Not Progressing to Clinical Status 6, 7, or 8 by Day 29

In the mITT population and among only those with an actual baseline ordinal score of 5, the proportion of subjects not progressing to ordinal score 6, 7, or 8 by Day 29 (see Section 3.3.4) will be analyzed using the same modeling approach as the primary outcome and described in Section 8.1.1. Kaplan-Meier curves (Figure 31) and p-values with estimates of proportions at the Day 29 study visit will be calculated and accompanied by confidence intervals (Table 23).

8.1.2.3. Mortality by Day 29

Mortality through Day 29 will be analyzed as a time to event endpoint (see Section 3.3.5). A table will present median time to event along with 95% confidence intervals overall for each treatment arm along with the hazard ratio estimate and log rank p-values. Differences in time-to-event endpoints by treatment will be summarized with Kaplan-Meier curves (Figure 27).

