P-value calculated using a stratified Chi-square test as in Klein 2007

^a[X] additional subjects are included in the 'Any Baseline Ordinal Score' row that were enrolled with an actual baseline ordinal score of 4. [Include as applicable]

Programming note: Subject may be listed in both Mechanical Ventilation by Day 29 and Dying by Day 29 columns if they required ventilation at any point prior to death. If Dying without ventilation, not included in both.

Table 16: Mechanical Ventilation Free Survival by Day 29 by Treatment Group and Actual Baseline Ordinal Score: Sensitivity and Exploratory Analyses – mITT Population, Actual Baseline Ordinal Score 5 or 6

Model	Treatment Group	Actual Baseline Ordinal Score	HR		Interaction P-value ^a
			Estimate	95% CI	
Covariate-Adjusted	Baricitinib + PBO + RDV (N=X)	Baseline Ordinal Score 5 or 6	x.xx	x.xx, x.xx	0.xxx
	PBO + Dexamethasone + RDV (N=X)		x.xx	x.xx, x.xx	
Treatment Arm-Baseline Ordinal Score Interaction	Baricitinib + PBO + RDV (N=X)	5	x.xx	x.xx, x.xx	0.xxx
	PBO + Dexamethasone + RDV (N=X)		x.xx	x.xx, x.xx	
	Baricitinib + PBO + RDV (N=X)	6	x.xx	x.xx, x.xx	
	PBO + Dexamethasone + RDV (N=X)		x.xx	x.xx, x.xx	
	Baricitinib + PBO + RDV (N=X)	Baseline Ordinal Score 5 or 6	x.xx	x.xx, x.xx	
	PBO + Dexamethasone + RDV (N=X)		x.xx	x.xx, x.xx	

HR is the ratio of the hazard of mechanical ventilation or death in each treatment group estimated from the indicated model. The ratio is PBO + Dexamethasone + RDV to Baricitinib + PBO + RDV.

HR for the Baseline Ordinal Score 5 or 6' group is the hazard ratio from the stratified Cox Model.

Covariate adjustment is by age, duration of symptoms prior to randomization, baseline d-dimer, and baseline CRP values as continuous covariates. High-sensitivity CRP values are excluded from this analysis.

Estimates are HR and CIs from interaction Cox models. For the interaction models, HRs are calculated at the level of each individual ordinal score category.

a P-values are from the likelihood ratio test.

Programming Notes:

For the “Treatment Arm-Actual Baseline Ordinal Score Interaction”, the ordinal score covariate will be treated as a categorical variable.

Tables with similar format:

Table 17: Mechanical Ventilation Free Survival by Day 29 by Treatment Group within Subgroups – mITT Population, Actual Baseline Ordinal Score 5 or 6

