Other Anti-Inflammatory Drugs	Baricitinib + PBO + RDV (N=X)	X.XX	X.XX, X.XX	--
	PBO + Dexamethasone + RDV (N=X)			
Covariate-Adjusted Model				
Covariate-Adjusted	Baricitinib + PBO + RDV (N=X)	X.XX	X.XX, X.XX	--
	PBO + Dexamethasone + RDV (N=X)			
Interaction Models				
Treatment-Continuous Actual Baseline Ordinal Score (5 or 6) Interaction	Baricitinib + PBO + RDV (N=X)	X.XX	X.XX, X.XX	--
	PBO + Dexamethasone + RDV (N=X)			

^aAnalysis of key secondary endpoint using those subjects in the mITT Population with actual baseline ordinal score of 5 or 6 with actual baseline ordinal score as a model covariate.

Odds ratios for interaction models are calculated at the level of each actual baseline ordinal score.

Programming Notes:

For the Main Analysis, the p-value will only be reported if the p-value from the primary analysis mechanical ventilation free survival is significant. If the p-value will not be reported, then the columns will be removed.

P-value of treatment comparison will only be displayed for the main analysis. For the interaction models, the p-value for the interaction term will be provided in a footnote reading “The p-value for the treatment by actual baseline ordinal score interaction term was 0.xxx.” or “The p-value for the treatment by continuous baseline ordinal score interaction term was 0.xxx.”.

For the covariate-adjusted model, the model will be run with age, duration of symptoms prior to randomization, baseline d-dimer, and baseline CRP values included as continuous covariates. High sensitivity CRP values are excluded from this analysis (denote this in a footnote).

Table with similar format:

Table 22: Odds Ratio for Better (Lower) Clinical Status Score at Study Visit Day 15 by Treatment Using a Proportional Odds Model, Baricitinib + PBO + RDV Relative to PBO + Dexamethasone + RDV – As Treated Population, Actual Baseline Ordinal Score 5 or 6

Programming Note: P-value of treatment comparison will only be displayed for the main analysis. For the interaction models, the p-value for the interaction term will be provided in a footnote reading “The p-value for the treatment by actual baseline ordinal score interaction term was 0.xxx.” or “The p-value for the treatment by continuous baseline ordinal score interaction term was 0.xxx.”.

Table 23: Proportion of Subjects Not Progressing to Clinical Status Ordinal Score 6, 7, or 8 by Day 29 by Treatment Group, Actual Baseline Ordinal Score 5

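### The covariate-adjusted Day 15 proportional odds model does not list baseline ordinal score, so as written it is not nested on the main model

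*SAP*

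**What the plan says.** **Main Day 15 model.** Under Section 8.1.2.1 the Day 15 score "will be analyzed using a proportional odds model with treatment arm and actual baseline ordinal score" (5 or 6) as covariates. Section 6.1 introduces its SAS code as "the proportional odds model with treatment arm and actual baseline ordinal score as covariates". Footnote a of Table 21 describes the main analysis as run "with actual baseline ordinal score as a model covariate"; that footnote is attached to the main-analysis row only.

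**Adjusted Day 15 model.** Two places define its covariates. Section 6.4 describes "regression modeling controlling for age, duration of symptoms prior to randomization, baseline d-dimer, and baseline CRP values as continuous covariates". The Table 21 programming note says "the model will be run with age, duration of symptoms prior to randomization, baseline d-dimer, and baseline CRP values included as continuous covariates". Table 22 (As Treated) is declared to share the format of Table 21, and its own note adds no covariate list. Section 8.2.2, on additional Day 15 analyses, does not describe the adjusted model.

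**Adjusted Cox models.** Section 8.2.1 and the notes to Tables 16 and 29 give the same four covariates. In both tables the covariate-adjusted row is labelled as baseline ordinal score 5 or 6, and a footnote says that the estimate for this "group is the hazard ratio from the stratified Cox Model". Table 21 has no comparable footnote for its adjusted row.

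**Stratification.** Section 4.2.3 stratifies randomization by site and by clinical status at enrollment (category 5 or 6).

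**The concern.** An adjusted analysis shown beside a main analysis should answer one question: does the estimate change when further prognostic covariates are added? That requires the adjusted model to contain everything in the main model. Read literally, the Table 21 note replaces ordinal score with four other covariates. Two things then change between adjacent rows, and a reader cannot tell which one moved the odds ratio.

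There is also a technical consequence. Odds ratios are not collapsible: leaving a prognostic factor out of a proportional odds model gives a different and smaller conditional odds ratio when treatment has an effect, even with perfect balance between arms. A reader could take such a shift for covariate imbalance. Two programmers could also fit different models from the same text.

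**Working it through.** The SAP states no figure for this model, so there is none to reproduce. The check has four steps.

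**1. How prognostic is the omitted factor?** The SAP gives no odds ratio for score 6 versus 5. Its Introduction gives ACTT-2 control-group median recovery times of 18 days on high-flow oxygen or non-invasive ventilation and 6 days on low-flow oxygen. Assuming exponential recovery times (an assumption made here), the proportion recovered 14 days after randomization is 1 − 2^(−14/median):
- low flow: 1 − 2^(−14/6) = 0.80, odds 4.04
- high flow: 1 − 2^(−14/18) = 0.42, odds 0.714

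The ratio is 4.04 / 0.714 ≈ 5.7, so prognostic odds of 4 to 8 are a reasonable working range.

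**2. Effect of leaving the score out, other things equal.** An 8-category proportional odds model was fitted at population level with and without ordinal score. The treatment odds ratio was set to 1.30, matching the ACTT-2 Day 15 estimate of 1.3 in the Introduction. The Day 15 distribution and the share of subjects with score 6 (20% to 50%) are assumptions. Loss is 1 − ln(OR without) / ln(1.30).

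| Prognostic odds, 6 vs 5 | OR without score (share 20% → 50%) | Loss on log scale |
|---|---|---|
| 2 | 1.295 → 1.292 | about 2% |
| 4 | 1.281 → 1.270 | 6% to 9% |
| 8 | 1.261 → 1.241 | 12% to 18% |
| 12 | 1.249 → 1.222 | 15% to 24% |

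For example, at 1.241: 1 − 0.216 / 0.262 = 0.18. With a true odds ratio of 1.00 there is no shift.

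**3. Efficiency.** A separate simulation used 1,380 subjects, 30% with score 6, log odds for score 6 versus 5 of −1.2 to −2.0, and one further prognostic covariate in both models (120 replicates per setting). The mean z fell from 2.66 to 2.47 (1 − 2.47/2.66 = 7%) and from 2.65 to 2.30 (13%). The loss is in z, not in a wider standard error. At an odds ratio of 1.30 and z of 2.66 the implied standard error is 0.262/2.66 ≈ 0.099. Without the score, at about 1.27 and z of 2.47, it is 0.239/2.47 ≈ 0.097.

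**4. Comparison with the row actually printed.** Table 21 sets the adjusted row beside a main row that contains ordinal score alone. Large simulated samples (100,000 to 200,000 subjects, true odds ratio 1.30) gave, for example:

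| Strength of each of the four covariates (log-odds per SD) | Prognostic odds, 6 vs 5 | Main (score only) | Four covariates only | All five |
|---|---|---|---|---|
| 0.15 | 8 | 1.279 | 1.237 | 1.287 |
| 0.4 | 2 | 1.263 | 1.300 | 1.302 |
| 0.4 | 8 | 1.275 | 1.252 | 1.303 |
| 0.6 | 2 | 1.223 | 1.290 | 1.296 |

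In all 12 settings the four-covariate odds ratio was below the five-covariate one, negligibly so where ordinal score was weakly prognostic (1.300 against 1.302). Against the main row it was lower in all six settings with weak covariates and higher in five of the six with stronger ones.

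**The case against.** The strongest reply is that the SAP is silent on the score rather than excluding it. Section 6.4 covers the primary and key secondary outcomes in one sentence with one list. For the primary outcome, Table 16 repeats that list and still indicates stratification by ordinal score, so there the list reads as what is added. Every proportional odds specification in the SAP includes the score, so reading the adjusted row as that model plus four terms is natural. This stands: a reader might infer that the plan deliberately removes the score, and the documents do not say so. It does not settle the matter. Where the SAP means the main model plus a term, as with the interaction model in Section 8.2.2, it says that the main analysis is repeated with that term included. The adjusted model has no such wording, and Table 21 lacks the footnote that rescues the Cox tables.

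A reader might also infer that Table 21 will show a weaker adjusted effect beside the main one. Step 4 does not support this: the direction depends on how prognostic the four covariates are.

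Finally, no decision depends on this row. Section 6.4 calls the analysis exploratory in effect, Section 8.2 places it outside the testing sequence, and the Table 21 note shows a treatment p-value for the main analysis only. All of that is correct and sets the weight of the point.

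**Conclusion.** The point holds in a limited form. The two places that define the covariates of the adjusted Day 15 model omit the stratification factor that the main model contains, and nothing elsewhere restores it. Run literally, the row is not nested on the main model and a difference between the two odds ratios cannot be attributed.

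Relative to the five-covariate model, and only if treatment has an effect, the odds ratio moves toward 1: for a true 1.30, to about 1.24 to 1.28, or 6% to 18% on the log scale, with some loss in z. These sizes rest on assumed prognostic odds of 4 to 8, an assumed share with score 6 and an assumed Day 15 distribution. The shift reflects a different conditional odds ratio, not confounding. The primary analysis, the main key secondary test and the fixed sequence are unaffected. This is a minor, free improvement.

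**What to change.** In Section 6.4 and the notes to Tables 21 and 22, state that the covariate-adjusted proportional odds model contains treatment, actual baseline ordinal score (5 or 6), age, symptom duration, baseline d-dimer and baseline CRP. For the Cox versions only a confirmation is needed: say in the text that the covariate-adjusted models remain stratified by actual baseline ordinal score, as the footnotes to Tables 16 and 29 indicate.

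The cost is one model term and one or two sentences, with no extra data. One limit remains: high-sensitivity CRP values are excluded from the adjusted analysis, so it may use fewer subjects than the main row. The number of subjects should be shown for each row.
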